Multicenter Prospective Randomized Control Study on Persona Total Knee System vs NexGen Total Knee System in Total Knee Arthroplasty

K.CR.I.EU.15.13

Protocol no.: 1.05

November 28th, 2016

Primary investigator

[name], Professor. (1) (Surgeon)

[name] (1) (Surgeon)

Investigators

[name] (1) (Surgeon)

[name] (2) (Surgeon)

[name] (3) (Surgeon)

[name] (4) (Surgeon)

[name] (5) (Surgeon)

Sponsor

Zimmer Biomet

Investigating institutions in Denmark

1) Dept. of Orthopaedic Surgery, Copenhagen University Hospital Hvidovre (1)

DK-2650 Hvidovre, Copenhagen, Denmark

2) Dept. of Orthopaedic Surgery, Vejle Sygehus, Sygehus Lillebælt (3)

DK-7100, Vejle, Denmark

3) Dept. of Orthopaedic Surgery, Farsø Sygehus, Ålborg Universitetshospital (4)

DK-9000, Aalborg, Denmark

4) Dept. of Orthopaedic Surgery, Næstved Sygehus, (5)

DK-4700, Næstved, Denmark

5) Dept. of Orthopaedic Surgery, Copenhagen University Hospital Gentofte, (6)

DK-2900, Hellerup, Denmark

Institution for radiographic data analysis and data collection

1) Dept. of Orthopaedic Surgery, Copenhagen University Hospital Hvidovre (1)

DK-2650 Hvidovre, Copenhagen, Denmark.

Study Synopsis

TITLE	Multicenter Prospective Randomized Control Study on Persona Total Knee System vs NexGen Total Knee System in Total Knee Arthroplasty
PROTOCOL NUMBER	K.CR.I.EU.15.13 (RCT)
STUDY DESIGN	Multicenter, 2-arm, randomized, controlled, single-blinded post-market study
STUDY OBJECTIVES / ENDPOINTS	Primary endpoint: Evaluate patient reported outcome measures following primary total knee replacement using Persona Total Knee system compared to NexGen total Knee System as measured by: Oxford Knee Score (3 months, 1 and 2 years postoperatively)
	 Secondary endpoints: Evaluate patient reported outcome measures following primary total knee replacement using Persona Total Knee system compared to NexGen total Knee System as measured by: Oxford Knee Score -Activity & Participation Questionnaire (APQ) anchoring questions, EQ-5D and Forgotten Joint Score (3 months, 1 and 2 years postoperatively).
	 Evaluate intra-operative and postop complications as well as long-term survivorship following primary total knee replacement using Persona Total Knee system compared to NexGen total Knee System as follows: Radiolucency / osteolysis at immediate postop 3 months, 1 and 2 year postoperatively. Adverse Events including intraoperative complications and revisions at any post-operative time points. Survival through registries at 5,7 and 10 years postoperatively.
INCLUSION/EXCLUSION CRITERIA	 Inclusion criteria: Patients with clinical and radiological osteoarthritis of the knee set to receive a primary unilateral total knee replacement >18 years of age Participants must be able to speak and understand Danish, able to give informed consent and be cognitively intact, able to complete all post-operative controls Participants must not have severe comorbidities, ASA score ≤ 3 Patients should be clinically suitable to receive a CR implant (no severe deformity and/or ligament instability) Exclusion criteria: Terminal illness Revision knee replacement surgery

	 RA Traumatic etiology Prior surgery on the affected knee that includes osteosynthesis, ACL and/or PCL and/or collateral ligament surgery. Arthroscopy with menisceotomy / cartilage surgery / house cleaning is allowed. Altered pain perception and / or neurologic affection due to diabetes or other disorders. Patients will be excluded intraoperative if CR implant is not suitable
SAMPLE SIZE	314 patients
LENGTH OF STUDY	Start/End-date: 2016 / 2029 (18 months enrolment, 2 years postoperative visits, up to 10 years postoperative follow-up in the registries)
INVESTIGATIONAL PRODUCTS	 Persona Total Knee System NexGen total Knee System Only cruciate retaining (CR) components will be used in this study. Both cemented and cementless femoral components Both standard as well as narrow femoral components Only cemented tibial components Conventional polyethylene will be used for patients >65 years old and Vitamin-E infused poly insert may be used for patients ≤ 65 years old. Resurfacing of patella is performed in all cases.
SCORES/PERFORMANCE ASSESSMENTS	OKS, OKS-APQ, EQ-5D, FJS, Patient satisfaction, ROM, X-rays (AP/lateral)
STATISTICAL REPORTING	 Using a two-sided t-test, 90% power and SD =10, 266 patients would be required. Accounting for a 15% drop-out 314 patients are planned to be enrolled. Non-inferiority analysis will be performed after 216 patients, based on OKS at one-year post randomization; MCID is set at 4 points. Using a one-sided t-test, 90% power and SD =10, non-inferiority margin of 4 OKS, 216 patients would be required for the NI analysis. The power calculation is based on reaching sufficient power when a comparison of the study groups is carried out.

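### The synopsis specifies no preoperative OKS, OKS-APQ or EQ-5D and plans unadjusted t-tests, giving up precision and a baseline check that cannot be recovered after surgery

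*Combined protocol and SAP*

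**What the plan says.** All references are to the Study Synopsis of the combined protocol and SAP.

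- **Study objectives / endpoints, primary:** "Oxford Knee Score (3 months, 1 and 2 years postoperatively". All three times are after surgery.
- **Study objectives / endpoints, secondary:** the OKS-APQ is listed together with "anchoring questions, EQ-5D and Forgotten Joint Score (3 months, 1 and 2 years postoperatively", again only after surgery.
- **Scores / performance assessments:** "OKS, OKS-APQ, EQ-5D, FJS, Patient satisfaction, ROM, X-rays (AP/lateral". This row gives no times, and the documents contain no visit schedule.
- **Statistical reporting, final comparison:** "Using a two-sided t-test, 90% power and SD =10, 266 patients would be required". Enrolment is set at 314 to allow for 15% drop-out.
- **Statistical reporting, non-inferiority:** a one-sided t-test of OKS at one year, with a 4-point margin, 90% power, SD 10 and 216 patients.

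The words preoperative and baseline do not occur in the documents. No change-from-baseline endpoint and no covariate is described.

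**The concern.** Patients come to knee replacement with different degrees of pain and disability, and some of that difference is likely to persist in the postoperative score. A t-test on postoperative OKS leaves this variation in the error term. If a preoperative OKS is available, entering it as a covariate removes part of that variation without adding patients.

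Two further uses are lost without such a score:

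- The report could not show whether the arms started at similar severity on the primary instrument.
- The plan allows for 15% drop-out, and patients found unsuitable for a CR implant are excluded during surgery. Someone lost before 3 months would have no scheduled OKS at all, so one could not check whether those lost were more or less severe than those analysed, or use their starting score in a missing-data analysis.

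Most gaps in an analysis plan can be filled before the database is locked. This one cannot: the opportunity ends at the operation.

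**Working it through.** **Inputs from the documents:** SD 10, difference or margin 4 points, power 90%, drop-out 15%, N = 266, 216 and 314.

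**Assumptions:** 1:1 allocation; 4 points as the difference for the two-sided test; alpha 5% two-sided for the final test and 5% one-sided for non-inferiority (no alpha is stated, but these values reproduce the plan's figures); correlation r between preoperative and postoperative OKS of 0.3 to 0.5. The documents give no value for r, so a range is shown.

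**Step 1. Reproduce the plan.**
- Final test, normal approximation: n per arm = 2 × (1.960 + 1.282)² × 10² / 4² = 131.4, so 132. The exact t-test gives a total of 264.6, so 133 per arm, or 266.
- Non-inferiority: n per arm = 2 × (1.645 + 1.282)² × 10² / 4² = 107.1, so 108 per arm, or 216. One-sided 2.5% would give 264 instead.
- Drop-out: 133 / 0.85 = 156.5, so 157 per arm, or 314.

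All three figures reproduce with no baseline score entering. The unadjusted design therefore delivers its stated power.

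**Step 2. Effect of adjustment on precision.** Under ANCOVA the residual SD is 10 × √(1 − r²). With 133 per arm, SE = residual SD × √(2/133), the 95% half-width is 1.96 × SE, and the equivalent unadjusted N is 266 / (1 − r²).

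| r | Variance removed | SE (points) | 95% half-width | Equivalent unadjusted N |
|---|---|---|---|---|
| none | 0% | 1.23 | 2.40 | 266 |
| 0.3 | 9% | 1.17 | 2.29 | 292 |
| 0.4 | 16% | 1.12 | 2.20 | 317 |
| 0.5 | 25% | 1.06 | 2.08 | 355 |

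**Step 3. Effect on power.**

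| r | Non-inferiority at 216, one-sided 5% (noncentral t) | Final test at 266, two-sided 5% (normal approximation) |
|---|---|---|
| none | 90.1% | 90.4% |
| 0.3 | 92.3% | 92.8% |
| 0.4 | 94.0% | 94.5% |
| 0.5 | 95.9% | 96.5% |

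**Step 4. Why ANCOVA and not change scores.** If both scores have SD 10, the SD of the change is 10 × √(2(1 − r)). The two-sided test would then need 368, 316 and 264 patients at r = 0.3, 0.4 and 0.5, against 264 for the postoperative score alone (normal approximation). A change score beats the planned test only when r exceeds 0.5. ANCOVA improves on the planned test at every value of r in the range.

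**The case against.** The strongest reply is that nothing planned is broken. Randomisation makes a comparison of postoperative OKS valid, the sample size was calculated for exactly that comparison, and no change-from-baseline endpoint is promised. This stands. The point concerns efficiency and interpretability, not validity.

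Three stronger readings are tempting, and the documents do not support them.

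- **That the trial has no starting score.** The times quoted belong to the endpoints row, which says when the arms are compared. That row is not a full schedule. Range of motion and patient satisfaction are listed as assessments with no time anywhere. Eligibility requires radiological osteoarthritis, although the only timed radiographic entries begin immediately after surgery. OKS and EQ-5D stand in the same untimed assessments row. The documents support only that no preoperative score is specified. Even if one is collected, the stated tests do not use it.
- **That the anchoring questions and the 4-point MCID are unusable without a baseline.** The secondary endpoint names only "Oxford Knee Score -Activity & Participation Questionnaire (APQ) anchoring questions"; their wording and use are not given. The synopsis says "MCID is set at 4 points" and uses 4 points as a between-arm margin, which needs no change score. It states no aim of validating an MCID.
- **That chance baseline imbalance is an extra error to be set against the margin.** Under randomisation such imbalance is already part of the standard error. The fair measure of the gain is the narrowing of the 95% half-width: 2.40 − 2.29 = 0.11 points at r = 0.3, and 2.40 − 2.08 = 0.32 points at r = 0.5.

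**Conclusion.** The point holds as a worthwhile, low-cost improvement. The synopsis specifies no preoperative OKS, OKS-APQ or EQ-5D, and both OKS comparisons are planned without a covariate.

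For r of 0.3 to 0.5, adjustment would be worth about 26 to 89 additional unadjusted patients (292 − 266 and 355 − 266) and 2 to 6 percentage points of power in each test. At r = 0.3 the gain is modest. The checks on starting balance and on severity among drop-outs come in addition and do not depend on r.

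The size rests on r, which the documents do not give, and on the assumed allocation ratio and alpha levels. That no preoperative score or covariate is specified rests on the text alone. Whether a preoperative score is in fact collected cannot be settled from these documents.

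**What to change.** 1. State in the protocol whether OKS, OKS-APQ and EQ-5D are completed before surgery. If they are not, add them, to be completed after consent and before the allocation is known.
2. Replace the two t-tests with an ANCOVA of OKS on arm and preoperative OKS. Use it for the one-year non-inferiority analysis, comparing the confidence limit of the adjusted difference with the existing 4-point margin, and for the final two-sided analysis. The planned 216, 266 and 314 can stay as they are.
3. Give a simple rule, set in advance and the same in both arms, for a missing preoperative score.
4. Report preoperative scores by arm, and compare them between patients analysed and patients lost or excluded during surgery.

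The cost is a few minutes of questionnaires per patient, some missing baselines to handle, and a short addition to the analysis text. No additional patients are needed. That no extra visit is needed is an assumption: informed consent implies some contact before surgery, but the documents do not describe it.

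### Does the rule that excludes patients in theatre when a CR implant is unsuitable break the randomised comparison?

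*Combined protocol and SAP*

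**What the plan says.** All the relevant text is in the Study Synopsis of the combined protocol and SAP.

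- **Inclusion criteria:** "Patients should be clinically suitable to receive a CR implant (no severe deformity and/or ligament instability". CR suitability is therefore judged once before surgery.
- **Exclusion criteria:** "Patients will be excluded intraoperative if CR implant is not suitable". This is a second, later judgement of the same property, listed with the eligibility rules.
- **Investigational products:** "Only cruciate retaining (CR) components will be used in this study". The restriction applies to both systems.
- **Study design:** "Multicenter, 2-arm, randomized, controlled, single-blinded post-market study". It does not say who is blinded.
- **Timing:** Statistical reporting places the non-inferiority analysis at one year, "based on OKS at one-year post randomization". The primary endpoint counts the same score from surgery: "Oxford Knee Score (3 months, 1 and 2 years postoperatively".
- **Sample size:** "Using a two-sided t-test, 90% power and SD =10, 266 patients would be required", raised to 314 for 15% drop-out. For non-inferiority: "non-inferiority margin of 4 OKS, 216 patients would be required for the NI analysis".

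The supplied text names no analysis set, does not describe how or when patients are allocated, and has no rule for a randomised patient who turns out to be unsuitable for a CR implant.

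**The concern.** A judgement made during surgery can fall after the patient has been assigned an implant. If it does, and patients judged unsuitable then leave the study, the groups compared are no longer the groups randomised. The surgeon makes the judgement and may know the assigned implant, since the type of blinding is not specified. If more patients with a poor prognosis were dropped from the Persona arm than from the NexGen arm, the Persona mean would be flattered. In a non-inferiority test, that raises the chance of a false claim. The opposite imbalance would cost power.

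The synopsis does not rule this out. One-year OKS is counted from randomisation in one place and from surgery in another. The two agree if randomisation is at or near surgery, but that fits allocation on either side of the CR decision.

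**Working it through.** **Inputs from the synopsis.** SD 10; a difference of 4 OKS points (the stated MCID, also the non-inferiority margin); 90% power; 266 patients for the two-sided test; 216 for non-inferiority; 15% drop-out; 314 enrolled.

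**Assumed, because not stated.** 1:1 allocation; two-sided alpha 0.05 for the main test; one-sided alpha 0.05 for non-inferiority; every exclusion rate and every OKS deficit below.

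**Step 1: reproduce the plan's figures.** Powers use the noncentral t distribution.

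- Two-sided test, 133 per arm: SE = 10 × √(2/133) = 1.226, power 90.1%. This agrees with 266.
- Enrolment: 266 / 0.85 = 312.9, so 313, or 314 as an even number. In reverse, 314 × 0.85 = 266.9.
- Non-inferiority, 108 per arm: SE = 10 × √(2/108) = 1.361. One-sided alpha 0.05 gives power 90.1%; alpha 0.025 would give 83.3%. So 216 corresponds to 0.05.

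**Step 2: what exclusion does if it follows randomisation.** Let e1 and e0 be the shares excluded in the Persona and NexGen arms, and let the gap be the OKS deficit of excluded against retained patients, taken as equal in both arms. Each retained mean exceeds its full-arm mean by e × gap, so the difference between arms shifts by

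shift = (e1 − e0) × gap.

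Equal shares give zero shift whatever the deficit.

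**Step 3: put numbers in for non-inferiority.** Excluded patients are taken off the arm concerned. Error is the chance of claiming non-inferiority when the true difference is −4. Power is at a true difference of 0.

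| Scenario (assumed) | Persona v NexGen | Shift | SE | Error | Power |
|---|---|---|---|---|---|
| No exclusions | 108 v 108 | 0 | 1.361 | 5.0% | 90.1% |
| Three per arm | 105 v 105 | 0 | 1.380 | 5.0% | 89.3% |
| 1-point excess in Persona, gap 5 | 107 v 108 | 0.01 × 5 = +0.05 | 1.364 | 5.4% | not needed |
| 3-point excess in Persona, gap 5 | 105 v 108 | 0.03 × 5 = +0.15 | 1.371 | 6.2% | not needed |
| 3-point excess in NexGen, gap 5 | 108 v 105 | −0.15 | 1.371 | 4.0% | 87.6% |

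A 3-point excess is 0.03 × 108 = 3.2, rounded to 3 patients. The shift of 0.15 is 0.15 / 4 = 4% of the margin.

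**Step 4: the two-sided test.** With 129 v 133 and a shift of 0.15, SE = 1.236 and the error goes from 5.0% to 5.2%.

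**Step 5: an extreme case.** An 8-point imbalance with a 10-point deficit shifts the difference by 0.08 × 10 = 0.8, a fifth of the margin. With 0.08 × 108 = 8.6, rounded to 9, patients removed from one arm, the non-inferiority error is 14.2% if they come from Persona. If they come from NexGen, it is 1.3% with power 74.1%. Nothing in the documents points to an imbalance of this kind between two CR-only arms screened for CR suitability. The case shows how far the inputs must be pushed before the error becomes serious, and carries no weight in the conclusion.

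**The case for a change.** The strongest case for acting does not need a large expected bias. The rule is unstated, the remedy is cheap, and follow-up that was never collected may be impossible to recover. If allocation already follows the CR decision, one sentence would say so. If it does not, keeping OKS follow-up on a few patients and listing exclusions by arm would let a reader check the balance. At assumed rates of 1% to 3% of about 157 per arm (314 / 2), that is roughly 2 to 5 patients per arm.

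The silence is real, and so is the low cost. Three things weaken the case.

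- **The defect is conditional.** No sentence puts randomisation before the decision. Listing the rule with the exclusion criteria fits a last eligibility check before allocation, though it does not prove one.
- **Only a synopsis is available.** Randomisation procedure, withdrawals and analysis sets usually belong in the body of a protocol, so their absence here does not show that the plan lacks them.
- **Keeping these patients in is not clearly better for non-inferiority.** The objective concerns outcomes of knee replacement with one system against the other. Patients without a study implant can dilute a true difference and so make non-inferiority easier to claim. Reporting the result both with and without them leaves open which one governs.

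It is also not stated whether losses in theatre fall within the 15% drop-out allowance. Step 3 takes them off the analysed number, which is the less favourable reading.

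**Conclusion.** No change to the plan follows. The synopsis leaves out the order of allocation and the intraoperative CR decision, and the handling of anyone randomised before it. That is a gap in detail, not a shown flaw in the design. If allocation follows the decision, the rule does no harm. If it precedes it, harm needs exclusions that differ by arm and patients whose outcomes differ from the rest. The documents give no sign that exclusions would differ by arm: both arms are limited to CR components and suitability is screened before surgery.

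Under modest assumptions the effect is small. Balanced losses leave the non-inferiority error at 5.0% and cost under one point of power. A 3-point excess in one arm with a 5-point deficit moves the error to 6.2% or 4.0%, depending on direction, and the two-sided error to 5.2%. These figures assume 1:1 allocation, the alphas that reproduce 216 and 266, and exclusion rates and deficits the documents do not supply. A trial run as written would probably still reach a sound conclusion. Analysts can close the gap in the ordinary way, by reporting when allocation took place and accounting for any patient randomised before an exclusion in theatre, by arm and reason. The conclusion would need another look if those counts proved clearly unequal.

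### Does the non-inferiority analysis lose its 90% power because the figure of 216 carries no drop-out allowance?

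*Combined protocol and SAP*

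**What the plan says.** Everything on this point is in the Statistical Reporting row of the Study Synopsis, which gives two sample-size statements.

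- **Two-sided comparison:** "Using a two-sided t-test, 90% power and SD =10, 266 patients would be required". The next sentence makes the allowance for loss: "Accounting for a 15% drop-out 314 patients are planned to be enrolled".
- **Non-inferiority:** "Non-inferiority analysis will be performed after 216 patients, based on OKS at one-year post randomization". The basis is "Using a one-sided t-test, 90% power and SD =10" with a "non-inferiority margin of 4 OKS", from which "216 patients would be required for the NI analysis".

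The minimal clinically important difference is also set at 4 points. The row ends by saying that the calculation aims at adequate power at the time the groups are compared. It gives no significance level, no time horizon for the 15% loss, and no statement of whether 216 counts randomised patients or patients with a one-year score.

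**The concern.** The two requirements look as if they are handled inconsistently. The 266 is inflated for drop-out and the 216 is not, yet 216 is both the calculated requirement and the point at which the analysis is run. It is also the smallest equal-arm total that reaches 90%, so there is no slack to absorb missing scores.

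If the analysis took the first 216 randomised patients at one year, some would have no OKS and power would be below the stated figure. The analysis uses the primary outcome measure. A failure to show non-inferiority could then reflect too few scores, while data from patients already enrolled were still to come.

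**Working it through.** **Inputs from the Statistical Reporting row:** SD 10, margin 4, power 90%, one-sided test for non-inferiority, two-sided test for the main comparison, drop-out 15%, enrolment 314.

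**Assumptions, because the text is silent:** true difference 0 under non-inferiority, 1:1 allocation, one-sided 5% for non-inferiority, two-sided 5% with a 4-point difference for the main comparison.

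**1. Reproduce 216.** Per arm, n = 2·SD²·(z₀.₉₅ + z₀.₉₀)² / margin² = 2·100·(1.645 + 1.282)² / 16 = 107.1, rounded up to 108, so 216 in total. The noncentral t calculation also gives 216, with power 90.06%. At one-sided 2.5% the requirement would be 264 (normal) or 266 (t), so 216 corresponds to one-sided 5%.

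**2. Reproduce 266 and 314.** A two-sided 5% t-test with difference 4, SD 10 and 90% power needs 133 per arm, or 266. Inflating per arm, 133/0.85 = 156.5, rounded up to 157, so 314 in total. All three printed figures therefore agree with the stated inputs, and 266 is clearly a count of patients with data, before drop-out.

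**3. Power if 216 counted randomised patients** (noncentral t, one-sided 5%):

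| Loss by one year | Scores available | Power |
|---|---|---|
| 0% | 216 | 90.1% |
| 5% | 216 × 0.95 = 205.2 | 88.7% |
| 10% | 216 × 0.90 = 194.4 | 87.2% |
| 15% | 216 × 0.85 = 183.6 | 85.4% |

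Rounding 183.6 up to 184 gives 85.5%. The last row needs the whole 15% to be lost by one year, although study visits run to two years.

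**4. Power if 216 counts patients with a one-year score.** It is 90.1%, with no inflation of the trigger needed. At 15% loss, 216 scores come from about 216/0.85 = 254.1 enrolled patients, so 255, or 256 for equal arms. Both are below 314. Full enrolment would give 314 × 0.85 = 266.9 scores.

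**5. Which reading the text supports.** Three features favour the second.
- The 216 and the 266 are presented in the same form, as numbers required, and 266 is a pre-drop-out count.
- The trigger is tied to the one-year OKS, so only patients with that score can contribute to a t-test on it.
- The closing sentence refers to power when the groups are compared, not when patients are enrolled.

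Against this, no text says that the 216 are the first patients or that they are randomised patients. The power loss depends on adding that.

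**The case for a change.** The best case for a change is that a trigger should have one reading. Counting randomised patients and counting available scores give different data cuts, different dates and different power, and leaving the choice open until data have accrued is untidy. Patients can also be excluded during surgery if the cruciate-retaining implant proves unsuitable, and the synopsis does not say whether they count towards the 216. One clause would settle the matter, and no extra patients would be needed.

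It is true that the counting unit is not written down. That is a missing detail, however, and not an arithmetic error. An analyst who sees 216 derived as the number needed for a t-test on one-year OKS would count patients who have that score, and then losses of any kind do not reduce the 216.

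The stronger remedies bring no clear gain. Waiting for every enrolled patient to pass one year would raise power to about 94.7% with 267 scores, but it gives up an earlier readout that the plan chose. With even accrual over the 18 months (an assumption), 254 patients are enrolled by month 254/314 × 18 = 14.6, so 216 scores are in hand at about month 26.6 at 15% loss, against month 30 for all patients. Restating the power as 85% would put a wrong figure in the plan if 216 counts scores.

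The unstated significance level is a separate matter. At one-sided 2.5%, power is 83.3% with 216 scores and 77% with 184, so about half of that fall from 90% comes from changing the level and not from drop-out.

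**Conclusion.** The concern does not show that the stated 90% power is wrong. On the reading the text favours, with 216 as the number of patients with a one-year OKS, power is 90.1% and the planned 314 patients supply about 267 scores at the plan's own 15% loss. A shortfall arises only if 216 means randomised patients. It would then be about 1 to 5 percentage points, with power of 88.7% to 85.4% for 5% to 15% loss by one year.

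These figures rest on one-sided 5% (inferred from 216 itself), a true difference of zero and equal allocation. They also rest on the synopsis row, which is the only statistical text available. What remains is an unstated counting unit that analysts would fill sensibly, and no result changes when they do.

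### Is the non-inferiority analysis at 216 patients run at too lenient a significance level?

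*Combined protocol and SAP*

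**What the plan says.** The only statistical text in the document is the Statistical Reporting row of the Study Synopsis. For the main comparison it says "Using a two-sided t-test, 90% power and SD =10, 266 patients would be required", followed by "Accounting for a 15% drop-out 314 patients are planned to be enrolled". For non-inferiority it says "Non-inferiority analysis will be performed after 216 patients, based on OKS at one-year post randomization; MCID is set at 4 points", and sizes that analysis with "Using a one-sided t-test, 90% power and SD =10, non-inferiority margin of 4 OKS, 216 patients would be required for the NI analysis".

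The Study Objectives / Endpoints row lists the primary measure as "Oxford Knee Score (3 months, 1 and 2 years postoperatively"), so one-year OKS is due from every patient and not only from the first 216. The Length of Study row gives the calendar: "18 months enrolment, 2 years postoperative visits, up to 10 years postoperative follow-up in the registries".

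Sidedness, power, SD, margin, endpoint and timepoint are thus given for non-inferiority. The synopsis does not give a significance level for either test, the allocation ratio, the true difference assumed under non-inferiority, or whether 216 counts enrolled patients or patients with a one-year score.

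**The concern.** A one-sided test without an alpha has no written decision rule. A reader of the synopsis cannot tell whether the lower limit of the 90% or of the 95% confidence interval has to clear -4 points.

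Working backwards, the two sample sizes appear to rest on different per-tail errors: 5% for non-inferiority and 2.5% for the two-sided comparison. The margin equals the MCID, so at the inferred level an implant worse by a full clinically important difference would be declared non-inferior 5% of the time.

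The plan also seems to hold a free remedy. One-year OKS is collected on everyone, and about 266 evaluable patients at one-sided 2.5% give the same 90% power. It looks as if the trial accepts double the error for nothing.

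**Working it through.** **Inputs from the synopsis.** SD 10; power 90%; margin 4; MCID 4; 314 enrolled; drop-out 15%; enrolment over 18 months; non-inferiority at one year.

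**Assumptions.** 1:1 allocation; true difference 0 for non-inferiority; a 4-point difference behind the 266, whose sentence names none.

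**Step 1: reproduce 216 and 266.** The normal approximation per arm is n = 2·SD²·(z_alpha + z_power)² / 4², that is 12.5·(z_alpha + 1.2816)².

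- One-sided 5%: 12.5·(1.6449 + 1.2816)² = 107.05, rounded up to 108 per arm, 216 in total.
- 2.5% per tail: 12.5·(1.9600 + 1.2816)² = 131.3, rounded up to 132 per arm, 264 in total.

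The t-test calculation uses the noncentral t distribution with noncentrality 4/(10·√(2/n)) and 2n − 2 degrees of freedom:

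| Per arm | Alpha | Power |
|---|---|---|
| 107 | one-sided 5% | 89.8% |
| 108 | one-sided 5% | 90.1% |
| 132 | two-sided 5% | 89.9% |
| 133 | two-sided 5% | 90.1% |

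So 216 is reproduced exactly at one-sided 5% and 266 exactly at two-sided 5%. For drop-out, 266/0.85 = 312.9, or 313, against 314 planned. In the other direction, 314 × 0.85 = 266.9 evaluable.

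**Step 2: how firm is the inferred alpha?** 216 would also give 90% power at one-sided 2.5% if Persona were assumed 0.43 points better. 266 would correspond to two-sided 0.117 at a 3.5-point difference, or 0.018 at 4.5. The synopsis states none of these. One SD, one power and one 4-point quantity explain both totals to the patient, so 5% one-sided and 5% two-sided is the simplest reading.

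**Step 3: compare the options.** Chance of declaring non-inferiority, SD 10:

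| True difference (Persona − NexGen) | 216, one-sided 5% | 266, one-sided 2.5% |
|---|---|---|
| 0 | 90.1% | 90.1% |
| −1 | 71.0% | 68.4% |
| −2 | 42.9% | 36.9% |
| −4 (at the margin) | 5.0% | 2.5% |

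With an observed SD of 10, the largest deficit that passes is 4 − 1.652 × 1.361 = 1.75 points for 216 at 5%, and 4 − 1.969 × 1.226 = 1.59 points for 266 at 2.5%. The rules differ by 0.16 OKS points.

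Two further combinations: 266 at one-sided 5% gives 94.6% power at a true difference of 0, and 216 at one-sided 2.5% gives 83.3%.

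**Step 4: what waiting costs.** With even accrual, 15% drop-out and 216 meaning evaluable, 216/0.85 = 254 must be enrolled. The 216 analysis then falls at 254/314 × 18 + 12 = month 26.6, and the full one-year data at 18 + 12 = month 30. The delay is 3.4 months (4.2 at 10% drop-out, 2.5 at 20%).

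**Step 5: slack.** The stricter test has 91.7% power at 10% drop-out (141 per arm) and 88.3% at 20% (125 per arm). At SD 11, power is 84.0% for 266 at 2.5% and 84.6% for 216 at 5%.

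**The case for a change.** The strongest case for a change is that alpha defines the test. If someone later reads a 95% interval at 216 patients, power is 83.3% and not the stated 90%. The wording on timing is also loose: if 216 means enrolled patients and 15% are lost, about 184 are evaluable (216 × 0.85 = 183.6), with power of about 85% at one-sided 5% or 77% at one-sided 2.5%. Halving the error at the margin needs no extra patient or visit, which makes keeping 5% hard to defend.

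Part of this stands. The synopsis would be clearer with alpha, the deciding confidence limit and the meaning of 216 written down. But these are gaps with an evident sensible filling. A number described as required for a test with 90% power is the number analysed, and only one-sided 5% gives 216 on the stated inputs without adding an assumed advantage for Persona. The text is also a synopsis, so the absence of alpha there does not show that the trial team had none.

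The call for 2.5% is weaker. A one-sided 5% test and a two-sided 5% test each carry 5% total error, and nothing in the plan ties the non-inferiority test to the per-tail level of the other. One-sided 5% is less strict, but it is not invalid.

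Nor is the alternative free. It removes an analysis deliberately scheduled ahead of full data. It also spends the 50 extra patients (266 − 216) on stricter error, when the same patients at one-sided 5% would raise power to 94.6%. Which of these to buy is a choice for the sponsor.

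**Conclusion.** The concern's arithmetic is right, but no change to the plan follows. No stated figure is wrong: 216 evaluable patients deliver 90.1% power at one-sided 5%, and 266 deliver 90.1% at two-sided 5%. The unstated alpha is a reporting gap that the plan's own numbers fill.

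Moving to one test on about 266 at one-sided 2.5% would lower the error at the margin from 5% to 2.5%. In exchange, the readout would come about 3.4 months later and the chance of a correct claim would fall by 2.6 percentage points at a true deficit of 1 (71.0% to 68.4%) and by 6.0 at a deficit of 2 (42.9% to 36.9%). That is a fair trade-off in either direction and does not correct an error.

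This rests on 1:1 allocation, SD 10, a true difference of 0 for non-inferiority, a 4-point difference behind 266, even accrual, 15% drop-out, and 216 meaning patients with one-year OKS.
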